2.3 Potential Risks & Benefits

2.3.1 Known Potential Risks

The following risks and discomforts may be experienced during participation in the study. In spite of all precautions, medical complications may occur. These include not only physical injury, but also possible psychological, social or economic harm, discomfort or inconvenience, or breach of confidentiality. To minimize risks, all study personnel are highly trained and experienced; materials are kept in locked file cabinets and are only available to investigators and research personnel associated with the study. All materials sent to outside laboratories are anonymized and the codes are kept with the NYU CBH Contact-PI ([name], MD). Both NYU's CBH and the Center for Healthful Behavior Change (CHBC), which will be a collaborator on this study to help provide expertise in recruitment strategies, have excellent records of safekeeping patients' data and have never had a breach of security. In the event of an adverse event at NYU or MSISC there are medical personnel available.

1. Physical, Neurological and Psychiatric Exams:

For the standard clinical examinations, there are minimal to no risks associated with the testing. The main risk is a loss of privacy and every precaution is taken to ensure confidentiality. Other psychological risks include discovering a condition that was not previously known.

2. Psychometric Testing:

There are no risks associated with cognitive testing. Some individuals may experience fatigue or test performance anxiety. Periodic breaks will be available during cognitive testing.

3. Laboratory Analysis of Blood:

The potential risks of blood drawing may occasionally include pain, bruising, fainting, or a small infection at the puncture site. Sometimes a small amount of bleeding into the arm (hematoma) may occur.

4. Heart Tracing (EKG):

The back of the electrodes are adhesive and may be uncomfortable when they are removed. There are no other risks associated with an EKG other than discovering a heart condition that was not previously known.

5. Genotyping:

There are potential dangers in obtaining DNA information. Genetic testing can generate information about a subject's personal health risks and can cause or increase anxiety, damage family relationships, and/or compromise insurability, employability and lead to social discrimination. To greatly reduce the possibility of such psychological or social risks, genetic results will be coded and no personal identification will link the subject with the genotype. Genetic results will not be disclosed to participants. We will include recommended language about the certificate of confidentiality and its limitations to the consent form.

6. MRI Scan:

MRI scanning involves the use of powerful magnets delivering radio frequency energy. Therefore, patients who have implanted metal devices, such as pacemakers, certain aneurysm clips, or shrapnel or metal in the eye, skull or elsewhere in the body are at risk. There are no known risks or adverse effects resulting directly from exposure to magnetic fields and radio frequency energy used in this study. Contrast agents are not used in this study. Some people feel claustrophobic in the MR or PET-MR scanners. The MR scanner produces loud tapping sounds during operation and earplugs are provided to all subjects. Other rare risks of MRI may include neuro-stimulation effects resulting in muscle twitches and tingling sensations, due to the rapid switching of magnetic fields, and a slight increase in body temperature that may occur in the presence and absorption of radio frequency energy. These are, however, very unlikely under current operational guidelines. In the very remote event that the magnet loses its magnetism, liquid

CONFIDENTIAL

helium in the magnet will be released. The room is designed with ventilation systems to prevent accumulation of these gases.

7. ^{11}C -Pittsburgh compound-B (PiB) PET-MR scan:

There is the possibility of discomforts associated with venous catheters. These risks include: minor pain or soreness, lightheadedness and/or minor bruising at the site of the catheter insertions, and less commonly, the formation of a small clot or swelling of the vein and bleeding. A chance of infection also exists. Experienced medical personnel will be involved in venipuncture procedure to minimize the possible risks associated with the catheters. As the effective dose (ED) of PiB is about 2.93 mSv when the recommended activity of 412 MBq of PiB is administered, adverse reactions due to radiation are expected to occur with a very low probability. In addition, PET/MR eliminates the exposure to CT scans used for attenuation correction by the PET/CT systems, so the radiation included would be lower than that of a similar study using PET/CT. Critical organ gallbladder wall exposure is 23.03 mGy. PiB is an experimental substance and other individual responses are possible and cannot be predicted. The frequency of allergic reactions to PiB is not known.

8. Sleep Studies:

The in-laboratory NPSG sleep studies are identical to those performed in clinical practice and present almost no risks as we will be using the standard diagnostic protocol for all subjects presenting to the MSISC with sleep complaints meriting a sleep study. The sleep study has no risks beyond the minor irritation that attachment of the recording electrodes on the skin occasionally may cause.

D. ADEQUACY OF PROTECTION AGAINST RISKS:

1. Recruitment, Informed Consent and Incidental Findings:

This study will involve male and female African-American elderly and white volunteer subjects with a diagnosis of 'cognitively normal' (CDR=0). Informed consent is obtained from each subject using IRB approved consent forms. In the consent form and in discussion with an investigator, participants will be advised fully of the procedures to be used, the amount of time required of them, the possible risks and benefits of the procedures, their right to refuse participation in the study without prejudice, their right to terminate participation at any moment without prejudice, and the name and telephone number of the Principal Investigators (Drs. [name] and [name]). In the informed consent form (ICF), participants will be told that the information they provide and all findings will be kept strictly confidential, with access limited to the research staff and the possible exception of state or federal regulatory personnel. Several steps will be taken to minimize reactions of discomfort, embarrassment, fatigue, or boredom.

Interviews will be conducted by staff that are well trained and closely supervised by [name]. The informed consent procedure explains the overall purpose of the study in straightforward terms, and explains the conditions of confidentiality. We encourage participants' questions and comments throughout the interview. For our questions about educational and cultural background, we emphasize that there is 'no right answer' to the questions. All participants are informed that they may refuse to answer any question and that they may discontinue the interview at any time without affecting their participation in the study or medical treatment. Participants are explicitly asked for their feedback, reactions, and strategies. Research staff that conduct follow-up interviews are blind to prior research diagnosis. All personnel of the study will have successfully completed the required education on protection of human research participants performed at NYU Langone Medical Center (NYULMC). In the ICF and in the discussion with members of the research team, participants will be advised that if the standard medical, neurological, or neuropsychological evaluation should uncover significant deficit or an emergent and previously undiagnosed medical condition, or if the blood assays reveal significantly abnormal findings, [name] will contact the participant to discuss the condition and, if permitted, contact the participant's physician or refer the participant to an appropriate medical professional for follow-up. A technician reviews each MRI scan as they are being acquired for major abnormalities. A licensed, board-certified radiologist will perform a safety review on every MRI scan and results will be communicated to study participants within 4 weeks of the date they are obtained. Findings of clinical significance, such as a mass, acute hemorrhage/infarct will trigger telephone notification of the subject by [name], MD and will inform them that an abnormal result has been found, and instructing them to contact their primary care physician (PCP). In addition, with

CONFIDENTIAL

This material is the property of the NYU School of Medicine and Langone Medical Center. Do not disclose or use except as authorized in writing by the study sponsor

permission, their PCP will be contacted and a report from the neuroradiologist will be sent to that physician. In the absence of clinically significant findings, the report of the neuroradiology review will be communicated to the participant in the form of a letter that describes the general findings; a more detailed radiological report is transmitted to the participant's PCP upon explicit request and retained in a permanent data base, but no direct telephone contact will be made. If the subject has no physician, and has a clinically significant finding, we will arrange for follow-up care at a local clinic.

2. Protection Against Risk:

a. PiB PET scans

PET-MR scanning involves the use of powerful magnets. Therefore, patients who have implanted metal devices, such as pacemakers, certain aneurysm clips, or shrapnel or metal in the eye, skull or elsewhere in the body are at risk. There are no known risks or adverse effects resulting directly from exposure to magnetic fields and radio frequency energy used in this study. Contrast agents are not used in this study. Some people feel claustrophobic in the PET-MR scanners. The MR scanner produces loud tapping sounds during operation and earplugs are provided to all subjects. Other rare risks of MRI may include neuro-stimulation effects resulting in muscle twitches and tingling sensations, due to the rapid switching of magnetic fields, and a slight increase in body temperature. These are, however, very unlikely under current operational guidelines. In the very remote event that the magnet loses its magnetism, liquid helium in the magnet will be released. The room is designed with ventilation systems to prevent accumulation of these gases.

Amyloid Pittsburgh compound B (PiB) tracer:

There is no recommended dose for PiB. 300 MBq is the lowest dose that has been recommended in the human studies published thus far (Klunk WE, Ann Neurol. 2004 Mar;55(3):306-19; Scheinin NM J Nucl Med. 2007 Jan;48(1):128-33), but most studies published to date include doses from 370 to 555 MBq (for a Cochrane review see Zhang S, Cochrane Database of Systematic Reviews 2014, Issue 7), with 370 MBq being the lowest injected dose below which the scan 'should not be performed and be rescheduled' according to the PET Technical procedures ADNI methods published in May 10th 2007 Version 1.2

[figure not shown]

Figure 1. PiB PET Scan

(http://www.adniinfo.org/Scientists/doc/PET_PiB_Tech_Procedures_Manual_Suppl_v1.3.pdf) Given the: i) heterogeneity in injected doses; ii) the heterogeneity in the current conduct and interpretation of the tests; iii) the lack of defined thresholds for determination of test positivity; iv) the plan of sharing the scans from this study with both the ADNI LONI Image Data Archive (IDA) and NACC Imaging; and; v) in the low signal to noise ratio (SNR) with 412 MBq injections in the first scans performed at NYU we have decided to follow ADNI methods and inject 555 MBq of PiB to increase the quality of the signal and the external validity of our findings, as well as future use of the data by outside groups

b. Clinical Studies and Labs

There are minimal physical risks associated with the standard diagnostic procedures. Moreover, there are minimal psychological risks to patients who participate in this study.

c. Sleep Studies

The in-laboratory sleep studies are identical to those performed in clinical practice. The sleep study has no risks beyond the minor irritation that attachment of the recording electrodes on the skin occasionally may cause. There is the possibility that sleep might be disrupted by the fact that subjects will be sleeping in a new environment. All data will be coded and stripped of identifiers to protect the confidentiality of the subjects. All sleep analyses and in-labs will be performed within the MSISC ([name]). MSISC has explicit emergency and procedure guidelines in place for dealing with medical emergencies that may arise.

CONFIDENTIAL

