On NPSG N2, participants will be trained in our published 3-D virtual maze spatial navigational test (see Figure 10)^{141;156}. Navigational memory represents a good model to study the effects of sleep-dependent memory consolidation. Rodent studies show that patterns of firing in hippocampal place cells during wake are replayed both in REM²²⁸ and NREM²²⁹ sleep. Behaviorally, sharp-wave ripple suppression impairs performance on a radial arm maze,²³⁰ while REM suppression impairs memory in the radial arm maze²³¹ and in the Morris water maze²³². In humans, overnight sleep enhances virtual maze navigation performance^{233;234}, while we have shown that maze completion time (CT) is attenuated after REM disruption¹⁷⁶ and is correlated with SWA in elderly subjects¹⁸⁸. Subjects will experience two different mazes at baseline and at the 2.5-year follow-up, and mazes will be counterbalanced across subjects for which maze is experienced first. Both mazes have been designed such that optimal CT is equivalent assuming perfect knowledge of the maze layout. Maze performance will be expressed as % change across sleep in maze CT compared to baseline CT before sleep. We have chosen a maze over a word-pair test^{105;235;236} because: 1) it taxes the hippocampus (more than a word-pair tasks would); 2) it's ecologically relevant to AD (*i.e.* spatial disorientation is one of the early clinical AD-symptoms); and 3) there are equivalent rodent models that lend insight into the underlying electrophysiological mechanisms (*i.e.* sharp-wave ripples, which cannot be captured with surface EEG).

Figure 10. Bird's eye view of virtual maze

PiB PET and MRI scans:

On visit 4, baseline and follow-up subjects will receive a single dose of 11.12 mCi PiB and perform a dynamic 60 min amyloid PiB PET-MR scan 35 min after injection.. The radioactive drug (PiB) shall meet appropriate chemical, pharmaceutical, and radionuclidic standards. The dose will be radioassayed proper to administration to ensure dosimetry data is correct. Further, the mass of the PiB is not expected to produce a pharmacologic response. PET/MR scans will be performed on an integrated 3T PET/MR

CONFIDENTIAL

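### The protocol gives two different injected PiB activities, 555 MBq and 11.12 mCi (411 MBq), and states the radiation dose only for the lower one

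*Combined protocol and SAP*

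**What the plan says.** Three places bear on the tracer activity.

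- **Section 2.3.1, item 7 (PiB PET-MR scan).** The effective dose is given as "about 2.93 mSv when the recommended activity of 412 MBq of PiB is administered", and from this the text concludes that "adverse reactions due to radiation are expected to occur with a very low probability". The paragraph adds: "Critical organ gallbladder wall exposure is 23.03 mGy". That sentence names no activity.
- **Section 2.3.1, Protection Against Risk, PiB tracer paragraph.** This denies that any dose of PiB is recommended and notes that "most studies published to date include doses from 370 to 555 MBq". It then lists reasons for a change, among them "low signal to noise ratio (SNR) with 412 MBq injections in the first scans performed at NYU", and concludes: "we have decided to follow ADNI methods and inject 555 MBq of PiB to increase the quality of the signal".
- **Section 6.1, PiB PET and MRI scans.** The procedure text says that "baseline and follow-up subjects will receive a single dose of 11.12 mCi PiB".

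**The concern.** The tracer paragraph and section 6.1 both say what will be injected, and they disagree. Both belong to the current body of the protocol; neither is an amendment log. One uses MBq and the other mCi, so the disagreement between them is easy to miss until the units are converted.

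As written, the protocol does not fix how much radioactive tracer a participant receives at each of two scans. If 555 MBq governs, the procedures section instructs the wrong activity, and the risk section gives no exposure figure for what is actually injected. If 11.12 mCi governs, the risk section announces a decision that was not carried out. Item 7 calls PiB experimental, and section 2.3.2 expects no direct benefit for most participants beyond payment. In that setting the activity and its exposure should be stated once and should agree.

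**Working it through.** **Inputs**

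- Activity in the tracer paragraph of section 2.3.1: 555 MBq.
- Activity in section 6.1: 11.12 mCi, at baseline and at follow-up (two scans).
- Effective dose in section 2.3.1, item 7: 2.93 mSv, stated for 412 MBq.
- Gallbladder wall dose in item 7: 23.03 mGy, no activity stated.
- Unit conversion: 1 mCi = 37 MBq.
- Assumption: dose is proportional to injected activity.

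The documents give no dose coefficient, so 2.93 mSv cannot be derived independently. What can be checked is which activity the figures agree with.

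**Step 1: common unit**

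- 11.12 × 37 = 411.4 MBq, which agrees with the 412 MBq of item 7 to within 0.14%.
- 555 / 37 = 15.0 mCi.

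Section 6.1 therefore matches item 7 and conflicts with the tracer paragraph.

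**Step 2: size of the gap**

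- 555 / 412 = 1.347, so 555 MBq is 35% higher. Rounding cannot explain this.
- Both values lie within the 370 to 555 MBq range that the protocol attributes to most published studies, so neither is an obvious typing error.

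**Step 3: effective dose**

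- Implied coefficient: 2.93 / 412 = 0.00711 mSv per MBq.
- At 411.4 MBq: 0.00711 × 411.4 = 2.93 mSv, the stated figure.
- At 555 MBq: 2.93 × 555 / 412 = 3.95 mSv (3.94 to 3.95 allowing for rounding of 2.93).
- Difference: 3.95 − 2.93 = 1.02 mSv per scan.

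| | 411–412 MBq | 555 MBq | Difference |
|---|---|---|---|
| One scan | 2.93 mSv | 3.95 mSv | 1.02 mSv |
| Two scans | 5.86 mSv | 7.89 mSv | 2.03 mSv |

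**Step 4: gallbladder wall**

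The figure names no activity, so both readings are shown.

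- If 23.03 mGy refers to 412 MBq, then at 555 MBq: 23.03 × 555 / 412 = 31.0 mGy.
- If 23.03 mGy already refers to 555 MBq, then at 412 MBq: 23.03 × 412 / 555 = 17.1 mGy.

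**The case against.** The strongest reply is that the tracer paragraph shows which text is current. It describes a sequence: 412 MBq was used in the first scans, the signal was poor, and 555 MBq was chosen. On that reading, section 6.1 and item 7 are leftovers. This is the likelier explanation, but it does not settle the matter, because section 6.1 is the procedure staff are told to follow. It also leaves the defect in place: section 6.1 would still order a superseded activity, and item 7 would still report exposure for it.

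A second reply is that the 35% depends on 2.93 mSv really belonging to 412 MBq, in a text that was evidently not edited consistently. That is fair as a condition. Item 7 does make the link explicitly. If the label were wrong and 2.93 mSv belonged to 555 MBq, the excess would vanish and the dose at 412 MBq would be 2.93 × 412 / 555 = 2.18 mSv. The documents offer no support for that reading, but the sponsor should confirm the figure.

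Third, the absolute difference is modest, and 555 MBq is within published practice as the protocol describes it. This stands: nothing here shows that radiation reactions cease to be very unlikely at 3.95 mSv. What is shown is a missing exposure figure and an unresolved activity.

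Finally, section 6.1 has each dose assayed before it is given. That measures the activity administered but does not say which target it should meet.

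**Conclusion.** The point holds. The current protocol specifies two activities that differ by 35%, does not reconcile them, and gives an effective dose for the lower one only. Followed to the letter, it either has participants injected with an activity that it says was set aside, or exposes them to about 3.95 mSv per scan against a stated 2.93 mSv (about 7.9 against 5.9 mSv over two scans). These figures assume that dose is proportional to activity and that 2.93 mSv belongs to 412 MBq, as item 7 says. The documents do not establish which activity is intended. The consent pages were not available, so what participants were told cannot be judged. Sample size and power are not affected.

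**What to change.** The sponsor should decide which activity applies and state it once, in one unit, in section 2.3.1 (item 7 and the tracer paragraph) and in section 6.1. Item 7 should then give the effective dose and the gallbladder wall dose for that activity, and name the activity to which 23.03 mGy refers.

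- **If 555 MBq governs:** change section 6.1 to 555 MBq (15.0 mCi) and restate the doses in item 7, with an effective dose of about 3.95 mSv per scan under proportional scaling.
- **If 11.12 mCi governs:** correct the tracer paragraph. The 2.93 mSv stands, subject to confirmation of its source.

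In either case, remove the clash between item 7, which calls 412 MBq recommended, and the tracer paragraph, which says no dose is. Check the consent form against the corrected text.

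The cost is a wording amendment, with IRB approval as section 11.2 requires. Design and analysis do not change. Practice at the scanner changes only if staff have been injecting an activity other than the one confirmed.

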2.3.2 Known Potential Benefits

Participants are made aware that the study does not provide clinical treatment and should not be used as a substitute for proper medical care with a physician; however, if the standard medical, neurological, or neuropsychological evaluation reveals significant deficit or an emergent and previously undiagnosed medical condition, or if the blood assays, or MRI scan reveal significant abnormalities, this information will be discussed with the participant and transmitted to their PCP. We do not expect the majority of participants to benefit directly from the research other than by financial remuneration for their time and effort. The potential benefits to society are considerable if this study reveals new information about new biological mechanism of AD risk in African-American elderly. Therefore, the risks to participants are reasonable in relation to the anticipated benefits to society.

3 Objectives and Purpose

3.1 Primary Objective

Aim 1 will test if African ancestry (%AF) is associated with short SWS duration and poor SWA in older AAs. **Challenge:** AAs consistently spend less time in SWS than whites²³⁻³². Although SWS shows significant heritability, social stressors may moderate these differences. **Approach:** test whether %AF⁴⁰ is associated with SWS characteristics after controlling for psychosocial factors (*e.g.* stress related to ethnicity). **Outcome:** positive results would suggest that racial differences in SWS have genetic underpinnings.

Aim 2 will test the effect of race and its interaction with baseline short SWS duration/poor SWA on longitudinal amyloid deposition. **Challenge:** AAs spend less time in SWS²³⁻³², a sleep stage important for A β dynamics⁴¹⁻⁴³ that may confer protection against amyloid deposition⁴⁴. **Approach:** assess how race is associated with longitudinal PiB uptake and its interaction with short SWS duration and poor SWA, after controlling for: 1) medial prefrontal (mPFC) atrophy, TST, AHI4% and cerebrovascular damage (measured as white matter lesion [WML] volume and abnormal diffusion kurtosis imaging [DKI] indices); and, 2) psychosocial factors, health care behaviors and medical morbidity. **Outcome:** reduced SWS/SWA would become a novel risk factor for AD in African Americans (AAs).

Aim 3 will test the effect of race and baseline poor SWA on cognition. **Challenge:** race and poor sleep have been associated with cognitive impairment. However, most studies are confounded by the inclusion of OSA patients, subjective measurements of sleep, lack of valid cognitive assessments for AAs and inadequate enrollment of minorities. **Approach:** we will test for the association between race and longitudinal changes in global cognition, memory, executive function and a sleep-dependent spatial navigational memory task. In addition, we will test their interaction with baseline SWA, using a similar approach as in Aim 2. **Outcome:** positive results would emphasize the importance of health messages promoting good sleep hygiene among AA elderly.

